defined by the protocol for 30 days or discharge whichever occurs first. Any Sunshine Heart field personnel or designee present for the implant procedure should review the informed consent prior to the procedure to ensure compliance.

In accordance with the ethical principles that have their origin in the Declaration of Helsinki, each patient must be informed about the study and the patient or legal representative must sign and date an agreement acknowledging that participation in the study is voluntary. The Patient Informed Consent Form will be provided to the patient in the language he/she is able to read and understand. (Refer to Appendix H for the sample Consent Form). The original signed Informed Consent will be retained in the individual Participant Study folders, and copies of the signed Informed Consent Form will be provided to the patient and to the hospital medical records of the patient.

Patients shall be consented for follow-up to 10 years.

Patient Withdrawal or Loss to Follow-Up

In the event a patient chooses to withdraw from the clinical study, the investigational site should attempt to ensure that any adverse events are resolved and documented as such. A Study Exit/Death Form must be completed and the patient will no longer be followed in the clinical study.

In the event the patient becomes lost to follow-up, the investigational site should make two documented attempts to contact the patient. A Study Exit/Death Form must be completed and the patient will no longer be followed in the clinical study.

Data Collection Overview

A review of patient files is required to determine preliminary eligibility according to patient inclusion and exclusion criteria. Baseline data including all imaging and functional test must be collected no more than **30** days prior to the implant date.

Follow-up data will be collected at the time of implant, hospital discharge, at planned follow-ups (1-month, 3-month, 6-month, 12-month, 18-month and annually from the implant date thereafter), and “unscheduled” follow-ups (device testing, patient symptoms requiring re-hospitalization, etc.). All adverse events will be collected throughout the study until closure.

Data will be collected via electronic data capture (EDC) screens referred to as e-case report forms (eCRFs). Echocardiogram tapes, and digital storage media must be documented in the patient medical record for source documentation.

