Device malfunction denotes a failure of one or more of the components of the MCSD system which either directly causes or could potentially induce a state of inadequate circulatory support (low cardiac output state) or death. The manufacturer must confirm device failure. A failure that was iatrogenic or recipient-induced will be classified as an Iatrogenic/Recipient-Induced Failure.

Device failure should be classified according to which components fails as follows:

- 1) **Pump** failure (implanted components of pump and any motor or other pump actuating mechanism that is housed with the implanted components). In the special situation of **pump thrombosis**, thrombus is documented to be present within the device or its conduits that result in or could potentially induce circulatory failure.

- 2) **Non-pump** failure (e.g., external pneumatic drive unit, electric power supply unit, batteries, controller, interconnect cable, compliance chamber).

Hemolysis

A plasma-free hemoglobin value that is greater than 40 mg/dl, in association with clinical signs associated with hemolysis (e.g., anemia, low hematocrit, hyperbilirubinemia) occurring after the first 72 hours post-implant. Hemolysis related to documented non-device-related causes (e.g. transfusion or drug) is excluded from this definition.

Hepatic Dysfunction

An increase in any two of the following hepatic laboratory values (total bilirubin, aspartate aminotransferase/AST and alanine aminotransferease/ALT) to a level greater than three times the upper limit of normal for the hospital, beyond 14 days post-implant (or if hepatic dysfunction is the primary cause of death).

Hypertension

New onset blood pressure elevation greater than or equal to 140 mm Hg systolic or 90 mm Hg diastolic (pulsatile pump) or 110 mm Hg mean pressure (rotary pump).

Major Infection

A clinical infection accompanied by pain, fever, drainage and/or leukocytosis that is treated by anti-microbial agents (non-prophylactic). A positive culture from the infected site or organ should be present unless strong clinical evidence indicates the need for treatment despite negative cultures. The general categories of infection are listed below:

Localized Non-Device Infection

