An adverse event will be considered related to patient management if it is a direct result of the medical complexities of managing the co-morbidities of heart failure.

Concomitant Medication Related

An adverse event will be considered related to concomitant medication when it is reasonable to believe that the event is directly associated with medications used in conjunction with the investigational device and it is not otherwise specific to the device, procedure or patient management.

Unavoidable Events

The events listed in Table 5 are considered minor and if the onset occurs within the timeframe specified, are not subject to adverse event reporting.

Table 5. Unavoidable Events

Event Description	Timeframe (post-implant)
Anesthesia related nausea/vomiting	24 hours
Low-grade fever (<102 degrees F)	48 hours
Minor incision/exit site pain	72 hours
Minor, localized tenderness, swelling, oozing, etc. at incision sites	72 hours
Early post-operative pain associated with endotracheal tube placement and mechanical ventilation	72 hours
Electrolyte imbalance without clinical sequelae	72 hours
Systolic and diastolic blood pressure changes that do not require treatment or intervention	On-going
Chest tube drainage or blood loss not requiring intervention and hematocrit remaining above 25%	72 hours
Sinus bradycardia and tachycardia that does not require intervention	On-going

Adverse Event Reporting to IRB and Regulatory Agencies for Unanticipated Device Events

The investigator must report any unanticipated adverse device effects (UADE) to the Sponsor (Sunshine Heart) and IRB within 10 days after the investigator first learns of the event. The Sponsor must report any UADE to the regulatory agencies, IRBs, and all investigators within 10 days of receipt of notice of the event.

An **unanticipated adverse device effect** is defined as:

Any serious adverse effect on health or safety or any life-threatening problem or death caused by, or associated with, the device, if that effect, problem or death was not previously identified in nature, severity, or degree of incidence in the protocol or application (including a supplementary plan or application), or any other unanticipated serious problem associated with a device that related to the rights, safety, or welfare of subjects. [21 CRF 812.3 (s)]

Patient Deaths

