This feasibility study intends to examine the effect of C-Pulse® on long-term heart failure, and to look for trends in performance indicators. This study is not powered to detect statistical significance. As such, clinical judgment is required to assess device safety and potential efficacy from data collected during this study. This clinical judgment will be provided by the DSMB.

Justification of Methodology

This study is designed as an open-label single-arm study to develop a further understanding of the C-Pulse®. It will provide safety and efficacy information for patients in whom C-Pulse® is implanted and maintain counterpulsation for six months or longer.

At six months post-procedure, the patients will provide an adverse event profile related to surgical placement of the C-Pulse® and six months employment of C-Pulse® counterpulsation. After six months of the study there will be additional information related to the adverse event profile. The patients will provide an adverse event profile for patients in whom C-Pulse® is placed and maintain counterpulsation for greater than six months.

Similarly, these patients will provide an efficacy profile. At six months post-procedure, the patients will provide information on how well a patient improves since baseline through six months of counterpulsation. After six months these patients provide additional efficacy information related to how well a patient improves since baseline through greater than six months of counterpulsation.

Primary Safety Measures

The safety of the C-Pulse® will be evaluated by reviewing a composite of the device-related adverse events through six months, as classified by the CEC. The composite device-related adverse event rate will be the percent of patients who experience at least one of the following adverse events as adjudicated by the CEC as device-related out of the total number of patients:

- Death
- Neurological Dysfunction
- Aortic Disruption
- Myocardial Infarction
- Major Infection
- Any other device-related adverse event (as adjudicated by the CEC)

The definitions for these adverse events are provided in the Adverse Event Definitions section.

Performance Requirements

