- Device & Equipment Disposition Logs, containing Site delivery dates of devices, implant dates and returned to Sponsor dates, quantities and serial numbers of devices delivered at the site, quantities and serial numbers of devices returned to Sponsor, expiration dates and patient IDs of the patients implanted.
- Signed Clinical Trial Agreement and current curriculum vitae.
- IRB documentation and correspondence.
- Center personnel training documentation forms.

INVESTIGATOR REPORTS

The investigator is responsible for the preparation (review and signature) and submission to the sponsor of all eCRFs, all death and adverse events (except unavoidable adverse events) and any deviations from the investigational plan; other reports are listed in [Table 6](#). All reports are subject to inspection and to the retention requirements described above for the investigator records.

If an IRB takes any action as a result of this study, copies of all pertinent documentation must be forwarded to the sponsor.

Table 6. Investigator Reports

Report	Submit to:	Description
Unanticipated Adverse Device Effect	Sponsor and IRB	If an unforeseen complication is determined to be related to the device, this information must be reported to FDA, IRB, and Sponsor.
Withdrawal of IRB Approval	Sponsor	The investigator must report a withdrawal of the reviewing IRB approval within 5 working days.
Progress Report	Sponsor and IRB	The investigator must submit this report if the study lasts more than one year on an annual basis.
Deviation from the Investigational Plan	Sponsor and IRB	The IRB and sponsor must be notified within 5 working days of the event of an emergency deviation from the IP to protect the life or physical well-being of a patient. Except for the deviations under emergencies, prior notification must be submitted to Sunshine Heart.
Failure to Obtain Informed Consent	Sponsor and IRB	The investigator must make notification within 5 working days after device use. The report must include a brief description of the circumstances justifying the failure to obtain informed consent and include written concurrence by a licensed physician not involved in the investigation.
Final Report	Sponsor and IRB	A final report must be submitted within 3 months after termination or completion of the study.

SPONSOR RECORDS

Sunshine Heart will retain the following records:

- All correspondence which pertains to the investigation.

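### The Hypertension event is defined by a pressure threshold alone, but Table 5 exempts blood pressure changes not needing treatment from reporting, so the reported Hypertension rate would not match its definition

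*Combined protocol and SAP*

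**What the plan says.** Under Adverse Event Definitions, Hypertension is "New onset blood pressure elevation greater than or equal to 140 mm Hg systolic or 90 mm Hg diastolic" for a pulsatile pump; a mean-pressure criterion is given for rotary pumps. The definition has no condition on treatment, duration or repeat measurement.

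Under Unavoidable Events, Table 5 lists minor events which, "if the onset occurs within the timeframe specified, are not subject to adverse event reporting". One row is "Systolic and diastolic blood pressure changes that do not require treatment or intervention". Its timeframe has no end, and the row sets no upper limit on the size of the change. Investigator Reports and Sponsor Records both repeat the exception for unavoidable events. The Data Collection Overview, by contrast, states without exception: "All adverse events will be collected throughout the study until closure".

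In the statistical section, Secondary Objectives asks for a rate and an exact two-sided 95% binomial interval for each event in the Adverse Event Definitions section, which includes Hypertension. Primary Safety Measures puts into the six-month composite any other event that the Clinical Events Committee (CEC) adjudicates as device-related, with no seriousness threshold. The CEC section says that the committee adjudicates events that are reported.

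**The concern.** The analysis takes its event definition from one section, while data capture follows an exemption in another. Neither text refers to the other, and no order of precedence is stated. A new-onset reading above the threshold that needs no treatment is a Hypertension event by definition but need not be reported.

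Two things follow. If every site applies Table 5, the table of adverse event rates shows a figure headed Hypertension that leaves out part of what the definition describes. If some sites report such readings on the strength of the definition and the general collection statement, the rate mixes two definitions. Either way, the estimate passed on to pivotal planning cannot be interpreted without knowing which rule was used.

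The gap is peculiar to this event. The Major Bleeding and Cardiac Arrhythmias definitions carry their own conditions on consequence or treatment, so the Table 5 rows on drainage and sinus rate do not collide with them. Where the protocol wanted a non-reporting rule for contrast-induced nephropathy, it put the rule inside the renal definition.

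**Working it through.** The documents give no expected rate for Hypertension or for the composite, so there is no plan figure to reproduce. The check is mainly a comparison of texts, followed by simple arithmetic.

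**Inputs.** Hypertension definition (Adverse Event Definitions); blood pressure row and reporting rule (Unavoidable Events, Table 5); interval type (Secondary Objectives); n = 20 (Sample Size Determination) and n = 40 (Design). I take the pulsatile-pump criterion as the one that applies.

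**Step 1: a test case.** Take a new-onset 150/95 at the 3-month visit, judged not to need treatment. Since 150 ≥ 140 and 95 ≥ 90, it meets the definition. It is also a blood pressure change needing no treatment, at a time the row covers, so Table 5 exempts it.

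**Step 2: where the texts disagree.**

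| Reading | Definition | Table 5 | Consistent? |
|---|---|---|---|
| New onset, at or above threshold, needs treatment | Event | Reportable | Yes |
| New onset, at or above threshold, no treatment needed | Event | Not reportable | No |
| Below both thresholds, no treatment needed | Not an event | Not reportable | Yes |

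The problem is confined to the second row.

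**Step 3: effect on the Hypertension rate.** Let a be the number of patients with at least one event needing treatment or intervention, and b the number whose only qualifying readings needed none.

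- Rate under the definition: (a + b)/n
- Rate under Table 5: a/n
- Difference: b/n, which cannot be negative, so Table 5 can only lower the rate
- Mixed site practice: (a + b′)/n, with b′ between 0 and b

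For b = 1 the difference is 1/20 = 5.0 points or 1/40 = 2.5 points. That holds for any single patient in any rate; it says nothing about how large b is.

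**Step 4: illustration with assumed counts.** The exact (Clopper–Pearson) limits for x of n are the 2.5% quantile of Beta(x, n − x + 1) and the 97.5% quantile of Beta(x + 1, n − x). I assume a = 2 at n = 20 and a = 4 at n = 40, and let b vary.

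| n | a | b | Rate a/n under Table 5 (95% CI) | Rate (a + b)/n under the definition (95% CI) |
|---|---|---|---|---|
| 20 | 2 | 2 | 10% (1.2–31.7) | 20% (5.7–43.7) |
| 20 | 2 | 4 | 10% (1.2–31.7) | 30% (11.9–54.3) |
| 20 | 2 | 6 | 10% (1.2–31.7) | 40% (19.1–63.9) |
| 40 | 4 | 4 | 10% (2.8–23.7) | 20% (9.1–35.6) |
| 40 | 4 | 8 | 10% (2.8–23.7) | 30% (16.6–46.5) |
| 40 | 4 | 12 | 10% (2.8–23.7) | 40% (24.9–56.7) |

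These counts are assumptions chosen to show the range, not forecasts.

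**Step 5: route to the primary composite.** An event of the second-row type changes the composite only if the site reports it despite Table 5, the CEC judges it device-related, and the patient has no other qualifying event through six months. If Table 5 is followed everywhere, such events would not ordinarily reach the CEC.

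**The case against.** The strongest reply is that the two texts do different jobs. The definition says what Hypertension is; Table 5 says what must be reported. The exemption is the more specific rule and is repeated in the sections on investigator reports and sponsor records, so a careful site would follow it. Excusing minor changes that need no treatment is a legitimate design choice. The CEC charter, which is not among the documents, may settle the matter. The study has no numerical performance goal: the DSMB judges the observed rates clinically, so no decision threshold is crossed.

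Most of this stands. A reader might infer that the plan flatly contradicts itself, with one reading both an event and not an event. The documents do not support that: an event that exists but is exempt from reporting is a coherent idea, and Table 5 reads naturally as governing reporting. What the reply does not answer is the analysis. Secondary Objectives asks for the rate of the event as defined and does not say that only cases needing treatment or intervention are counted.

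A reader might also infer that the readings are probably device-related, because counterpulsation raises diastolic pressure, and so distort the primary composite. The Background does describe diastolic augmentation, but also a reduction of aortic pressure before systole. The intra-operative study in Appendix E found no significant blood pressure change, though in six patients and acute use only. The eligibility limit helps little: systolic pressure up to 140 mmHg is allowed and no diastolic limit is set, but no baseline distribution is given, and a patient entering at 140 is already at the threshold.

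**Conclusion.** The point holds for the Hypertension rate. Followed as written, the plan undercounts the event it defines, or counts it differently across sites. The direction is known: Table 5 lowers the rate or leaves it unchanged. The size is b/n, that is 5.0 or 2.5 points per affected patient, and b cannot be determined from the documents. This rests on taking the pulsatile criterion as applicable and the 20 or 40 implanted patients as the denominator.

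Any effect on the primary composite is conditional on the three steps above, none of which the documents establish, and should not be claimed as a bias in that endpoint. This is a minor fault in a secondary descriptive safety rate, but more than a missing detail, because two stated rules give different counts for the same table entry.

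**What to change.** Reconcile the two texts in one of two ways:

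1. Limit the Table 5 blood pressure row to changes that do not meet the Hypertension definition. All threshold events are then reported, and the rate matches the definition.
2. Write the Table 5 exemption into the Hypertension definition, and label the rate in Secondary Objectives as hypertension requiring treatment or intervention.

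Apply the chosen rule at every site and state it in the CEC charter. As a descriptive check, tabulate patients with new-onset readings at or above the threshold, using the blood pressures already scheduled in Table 3 and at device checks. That tabulation will miss readings taken between visits, but it is free of site reporting practice.

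The cost is a sentence or two, a small extra table and, under the first option, possibly a less favourable Hypertension rate. No new measurement is needed, and the change concerns reporting only, not the management of blood pressure.

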Should the patient be re-hospitalized at any time post index hospitalization, the Unscheduled Follow-up Form should be completed. While hospitalized, the Follow-up Forms will continue to capture data and adverse events should be documented on the adverse event forms should they occur. When the patient is discharged again, the patient should be assessed per the discharge criteria to ensure they continue to meet the criteria.

Post-Implant Follow-up Testing and Data Collection

Post-Implant Testing and Data Collection Summary

The complete reference list of post-implant testing and data collection that will be performed at each time point is included in Table 3.

Unscheduled Follow-up Visits

If patients are seen between protocol-scheduled visits because of clinical symptoms requiring readmission, device reprogramming, etc. a follow-up form must be completed with all appropriate sections. In addition, all adverse events must be documented throughout the study.

System Modifications

Immediately contact Sunshine Heart clinical support team if a need is suspected for system modification (component or system replacement). In the event that the C-Pulse® System requires modification (e.g. Cuff or PIL) a System Modification Form should be completed along with an adverse event form. Modifications should be done only in communication with Sunshine Heart Service personnel, unless the modification is a medical emergency. In which case, Sunshine Heart personnel should be notified as soon as possible. In addition, the System Modification Form should be completed documenting the removal of the existing device or component. The C-Pulse® component(s) should be processed according to the Explant Handling Instructions and returned to Sunshine Heart or designee.

In the event of a system modification, including component removal, reposition or replacement of the entire C-Pulse® system, the follow-up schedule for the patient will remain unchanged (i.e. the patient should continue to be seen for follow-up and associated forms should be completed based on the original follow-up schedule). All adverse events should be reported and classified by the investigator. Additionally the CEC will provide further classification of adverse events.

Adverse Event Reporting

Overview

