All patient deaths must be documented on the Study Exit/Death Form. If the patient dies during the study, notify the Sunshine Heart field support personnel as soon as possible upon first learning of the death. Follow any IRB requirements for reporting of deaths or adverse events.

In the event of a patient death, efforts should be made to retrieve the implanted device and to obtain an autopsy in order to assess the state of the heart and aorta. A sample of the aorta beneath the C-Pulse® Cuff should be collected for analysis. Please call Sunshine Heart Clinical Support for more instruction. For patients who do not undergo autopsy, written documentation from the investigator will be required regarding circumstances as to why an autopsy was not performed. The device will be analyzed by local staff and Sunshine Heart clinical support personnel according to a standardized device retrieval protocol.

A death summary and an autopsy report are required, please send upon completion to Sunshine Heart to provide to the adjudication committee.

Explant Handling and Final Device Disposition

Promptly call Sunshine Heart Clinical Support for instruction regarding Explant Handling. Cultures should be taken from the device implantation site along with visual analysis and photographs when possible. Explanted products should be returned to Sunshine Heart for analysis.

Complete the Study Exit/Death Form. Report all associated adverse events. Update the Device & Equipment Disposition Log with all products. If the device is not returned to Sunshine Heart, justification must be provided in the log.

Patient Withdrawal and Study Exit

A Study Exit/Death Form shall be completed if patient is unable to or refuses to continue participation in the study. Notify the Sunshine Heart clinical support team as soon as possible upon learning of a patient withdrawal/study exit.

If the patient fails to comply with follow-up visits, the study center must make repeated attempts to contact the patient. Each attempt to contact the patient must be documented in the patient's records and on the Study Exit/Death form.

If the patient officially withdraws from the study, the investigator will document the reason for withdrawal and indicate any relationship of the withdrawal to the study or the device on the Study Exit/Death form.

If a patient withdraws from the study at any time, there will be no penalty or loss of future medical care.

STATISTICAL METHODS AND DATA ANALYSIS

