Additional Comments:

- No ointment or cream should be used at any time on the percutaneous lead of the C-Pulse unless directed to do so by the surgeon (no other physician).
- Inspect the Driver Carry Bag to be sure the integrity of the Velcro strap used to coil the Driver Lead.
- Take digital photos of the exit site to document the condition for future reference.

Infection Advisory Committee Recommendations:

Due to the possible interaction of site infection leading to “Deep” infection or tissue swelling around the intrathoracic gas line and /or ascending aorta an infection procedure monitoring process is recommended. The following process is recommended to reduce risk of injury to the patient.

Infection Monitoring Process:

In the presence of clinical signs (pain, redness, discharge, loss of driveline fixation) and /or microbiological evidence (positive wound culture) of infection (intermittent or chronic) over a 3 month period despite treatment.

Decision Process:

Are there clinical signs or microbiological evidence of infection over a 3 month period despite treatment?

- No: Continue therapy
- Yes: Perform CT or PET scan
 - If scan is positive (i.e. shows evidence of DEEP infection or soft tissue swelling around the intrathoracic gas line and/or ascending aorta or presence of intrathoracic gas), then REMOVE PIL AND CUFF.
 - If scan is negative (i.e. shows no evidence of DEEP infection), REMOVE PIL only.
 - If at the time of surgery there is clinical evidence of DEEP infection (i.e. pus or fluid around the ‘Y’- connector, positive gram stain, and infected tissue) then REMOVE the CUFF also.
 - If at the time of CT/PET scan or surgery there is no evidence of DEEP infection, then REPEAT SCAN at 3 months post-op and monitor for clinical signs of infection, if none found then REPEAT SCAN annually.
 - NOTE: If wound culture is positive for MRSA, MSSA or Pseudomonas, monitor more frequently with FOLLOW-UP CT-SCAN at 3 months.

Aortic Tissue Sampling Guideline

In the event of a heart transplant, LVAD or patient death it is recommended that the C-Pulse system be removed. To ensure evaluation of the system and patient interaction the following process provides guidance on removal of the C-Pulse implanted components at the time of explant, the observations to be recorded and for device return for analysis.

- If possible, return the devices intact and connected. In the event of device dissection, attempt to maintain the connections intact.

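### The protocol conflicts on whether a living patient whose device is removed stays in follow-up, and the six-month analysis has no rule for that patient

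*Combined protocol and SAP*

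**What the plan says.** Three sections of the protocol bear on a living patient who loses all or part of the device.

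- **System Modifications.** For a modification, "including component removal, reposition or replacement of the entire C-Pulse® system", the protocol states that "the follow-up schedule for the patient will remain unchanged". Sites are also told that "the System Modification Form should be completed documenting the removal of the existing device or component", and that the parts taken out "should be processed according to the Explant Handling Instructions and returned to Sunshine Heart or designee".
- **Explant Handling and Final Device Disposition.** After the instructions on cultures and device return, sites read: "Complete the Study Exit/Death Form. Report all associated adverse events". Partial removal, full removal in a living patient and removal at death are not distinguished.
- **Patient Withdrawal or Loss to Follow-Up.** For both situations in its title: "A Study Exit/Death Form must be completed and the patient will no longer be followed in the clinical study".

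Appendix U shows that removal in living patients is foreseen. With persistent signs of infection and a positive scan the instruction is "then REMOVE PIL AND CUFF". Where no deep infection is found, it is "then REPEAT SCAN at 3 months post-op and monitor for clinical signs of infection", with annual scans after that.

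On analysis, Primary Safety Measures counts patients with at least one device-related event through six months, as adjudicated by the events committee, over all patients. Subjects for Analysis makes the primary set everyone in whom a device was placed. The efficacy section compares baseline with month 6 and gives no rule for a patient without a month-6 value.

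**The concern.** A site that removes a lead or cuff from a living patient is told both to keep the visit schedule and to fill in the form that elsewhere ends follow-up. Sites may resolve this differently.

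Exit at explant would not be random. Appendix U links removal to infection, transplant, LVAD or death, so the patients lost would be those for whom the device had stopped working out. Their six-month efficacy values would be missing, and deaths or other events between exit and month 6 could go unrecorded. The monitoring board judges trial success on these rates, and Sample Size Determination says the estimates will be used to power the pivotal study.

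Two other phrases leave room to set such patients aside. Justification of Methodology describes the results as applying to patients who keep counterpulsating for at least six months. The secondary analysis set is defined by having been followed.

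**Working it through.** **1. The instructions side by side**

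| Situation (living patient) | System Modifications | Explant Handling | Result |
|---|---|---|---|
| One component removed | Schedule unchanged; removed part goes through explant handling | Exit form, no exception | Direct contradiction |
| Whole system replaced | Schedule unchanged | Exit form, no exception | Direct contradiction if the removed parts trigger explant handling |
| Whole system removed, not replaced | Not clearly named | Exit form, no exception | Only the exit form applies |

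The link comes from System Modifications itself, which sends removed parts into explant handling.

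**2. Inputs**

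- N = 20 implanted (Sample Size Determination) and N = 40 implanted (Study Size and Duration).
- Exact two-sided 95% binomial intervals (Performance Requirements). For x of n, the lower limit is the 0.025 quantile of Beta(x, n−x+1) and the upper limit is the 0.975 quantile of Beta(x+1, n−x). The lower limit is 0 when x = 0.
- The plan states no power, expected event rate, responder rate or explant rate, so there is no figure of its own to reproduce. The counts below are assumptions.

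**3. Responder percentage**

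Assume a 50% responder share over all implanted, with k patients explanted and exited before month 6, none of them a responder. Keeping them gives r/N; dropping them gives r/(N−k).

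| N | k (share) | All implanted | Explanted dropped | Rise |
|---|---|---|---|---|
| 20 | 1 (5%) | 10/20 = 50.0% (27.2–72.8) | 10/19 = 52.6% (28.9–75.6) | 2.6 points |
| 20 | 2 (10%) | same | 10/18 = 55.6% (30.8–78.5) | 5.6 points |
| 20 | 4 (20%) | same | 10/16 = 62.5% (35.4–84.8) | 12.5 points |
| 40 | 2 (5%) | 20/40 = 50.0% (33.8–66.2) | 20/38 = 52.6% (35.8–69.0) | 2.6 points |
| 40 | 4 (10%) | same | 20/36 = 55.6% (38.1–72.1) | 5.6 points |
| 40 | 8 (20%) | same | 20/32 = 62.5% (43.7–78.9) | 12.5 points |

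These are the largest rises for each explanted share at a 50% responder share. If half of the explanted patients had responded, dropping them would leave the percentage unchanged.

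**4. Safety composite**

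Assume 25% of patients have a device-related event, including the events that led to explant. Those events are to be reported, and the denominator is all patients. The rate is therefore 5/20 = 25.0% (8.7–49.1) or 10/40 = 25.0% (12.7–41.2), whether or not the patient then exits.

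**5. What exit can hide**

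Performance Requirements calls for deaths between 30 days and 6 months as a separate line. If the only such death occurs after exit and is missed:

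- N = 20: 1/20 = 5.0% (0.1–24.9) becomes 0/20 = 0% (0–16.8).
- N = 40: 1/40 = 2.5% (0.1–13.2) becomes 0/40 = 0% (0–8.8).

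The composite itself changes only if the missed event would have been the patient's first device-related event.

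**The case against.** The strongest reply is that the sections describe different situations: modification while the device stays in use, and final disposition once its use has ended. The explant section sits between Patient Deaths and Patient Withdrawal and Study Exit, and its title speaks of final disposition. The sentence ending follow-up was written for withdrawal and loss to follow-up. The form also has another use, since contact attempts are recorded on it. The rationale for Version 9 in Appendix V, follow-up of patients with a full or partial system, suggests that partial removals were meant to stay in the study.

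This narrows the point without removing it. Patient Deaths already requires the form for every death, so a death-only reading would make the explant instruction redundant. System Modifications itself leads into explant handling, where no exception is stated. The Version 9 rationale supports the reading that exit was not intended for partial removals, which is a reason to correct the instruction.

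Three further objections stand:

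- The missing rule for patients without a month-6 value is a gap whatever the reason for missingness, so correcting the form alone would not settle the denominator.
- The infection pathway in Appendix U starts only after signs persist over three months despite treatment, which limits how many such explants can fall before month 6.
- In the efficacy section a non-responder is a patient with measured decline past a threshold. Putting unmeasured patients there would overstate decline.

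**Conclusion.** The instructions conflict for component removal. For full explant of a living patient without replacement, they leave only an exit form. If sites follow that form, patients explanted before month 6 have no six-month efficacy values, and deaths or first device-related events between exit and month 6 can be missed.

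A reader might infer that the worst device outcomes drop out of the six-month safety composite. The documents do not support that. The event behind an explant is to be reported; if adjudicated device-related, it counts that patient once over all patients, and the as-treated set keeps everyone in whom a device was placed.

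The 2.6 to 12.5 point rise in the responder percentage rests on three assumptions: 5–20% of implanted patients explanted and exited before month 6, none of them responders, and all of them dropped from the denominator. The documents neither direct nor prevent the last. No published figure in the plan is wrong. The point should be corrected because the remedy is cheap and the rates feed both the board's judgment and the pivotal design.

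**What to change.** - **Forms.** Reconcile System Modifications with Explant Handling. Use the System Modification Form for any living patient with partial or full explant. After implant, limit the Study Exit/Death Form to death, withdrawal of consent or loss to follow-up.
- **Follow-up.** State that living explanted patients, including those who go on to LVAD or transplant, remain in adverse-event and vital-status follow-up on the existing schedule.
- **Denominators.** In the statistical section, state that all implanted patients form the denominator of the six-month safety and responder percentages. Align the wording in Justification of Methodology and Subjects for Analysis with this.
- **Classification.** Count a patient explanted before month 6 as not achieving response, in a separate category (explanted, no on-device value). Keep this apart from the existing non-responder and indeterminate classes. It also covers an LVAD or transplant patient whose month-6 value would reflect another therapy.
- **Sensitivity analysis.** Repeat the responder analysis in patients still on the device at month 6.

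The cost is a wording and form change, continued contact with a few patients (already required after component removal), and a slightly less favourable responder percentage. None of this sets or alters a clinical rule on when a device is removed.
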